8. SECONDARY STATISTICAL ANALYSES

8.1. Secondary Pharmacokinetic Analyses

8.1.1. Overview of Planned Secondary Pharmacokinetic Analyses

The secondary pharmacokinetic (PK) analyses will be based on the Injection (Week 89) PK population, unless otherwise specified.

Table 11 provides an overview of the planned analyses, with full details being presented in Appendix 14: List of Data Displays.

Table 11 Overview of Planned Secondary Pharmacokinetic Analyses

Display Type	Untransformed						Log-Transformed									
	Stats Analysis			Summary			Individual		Stats Analysis			Summary			Individual	
	T	F	L	T	F	L	F	L	T	F	L	T	F	F	L	
Oral/Injection																
PK Concentrations				Y	Y ^[1]	Y ^[1]	Y									
Plasma PK Parameters	Y			Y			Y			Y	Y					

NOTES:

- T = Table, F = Figure, L = Listings, Y = Display generated.
- Stats Analysis = Represents TFL related to any formal statistical analyses (i.e. modelling) conducted.
- Summary = Represents TFL related to any summaries (i.e. descriptive statistics) of the observed raw data.
- Individual = Represents FL related to any displays of individual subject observed raw data.

^[1] Linear and Semi-Logarithmic plots will be created on the same display.

8.1.2. Secondary Drug Concentration Measures

Refer to Appendix 5: Data Display Standards & Handling Conventions (Section 10.5.3 Reporting Process & Standards).

8.1.3. Secondary Pharmacokinetic Parameters

8.1.3.1. Deriving Secondary Pharmacokinetic Parameters

- Refer to Appendix 5: Data Display Standards & Handling Conventions (Section 10.5.3 Reporting Process & Standards).
- The pharmacokinetic parameters will be calculated by standard non-compartmental analysis according to current working practices and using Phoenix WinNonlin Version 6.4 or higher.
- All calculations of non-compartmental parameters will be based on actual sampling times, and all concentrations will be included in the estimation of PK parameters regardless of whether samples are collected within the specified time window or not.
- Pharmacokinetic parameters described in Table 12 will be determined from the plasma concentration-time data, as data permits.

Table 12 Derived Secondary Pharmacokinetic Parameters

Parameter	Parameter Description
AUC(0- τ)	Area under the concentration-time curve over the dosing interval will be calculated using the linear trapezoidal rule for each incremental trapezoid and the log trapezoidal rule for each decremental trapezoid.
C _{max}	Maximum observed concentration, determined directly from the concentration-time data.
t _{max}	Time to reach C _{max} , determined directly from the concentration-time data.
C _{τ}	Observed concentration at the end of the dosing interval, determined directly from the concentration-time data.
t _{1/2}	Terminal absorption elimination half-life will be calculated as: $t_{1/2} = \ln 2 / \lambda_z$
λ_z	Terminal absorption elimination rate constant
CL/F	Clearance (adjusted for bioavailability, F) will be calculated as: $CL/F = \text{Dose} / AUC(0-\tau)$
V _z /F	Volume of distribution (adjusted for bioavailability, F) will be calculated as: $V_z/F = CL / \lambda_z$

NOTES:

- Additional parameters may be included as required.

8.2. Safety and Tolerability Analyses of Oral CAB

The safety and tolerability analyses of oral CAB will include Grade 2 or higher clinical and laboratory events occurred during the oral phase. Analysis time frame is from the first date of taking oral CAB tablet to the date right before the first CAB LA injection. For subjects who withdraw treatment from the oral phase, the analysis will include all safety and tolerability assessments from the first date of taking oral CAB tablet up to the date of last study visit.

Safety endpoints including adverse events, laboratory test, vital signs, and death will be analysed. The same analysis approaches will be conducted as in the primary analysis, but with different time frame.

[Table 13](#) provides an overview of the planned analyses, with full details of data displays being presented in [Appendix 14](#): List of Data Displays.

Table 13 Overview of Planned AE, LB, VS, and Death Analyses

Display Type	Data Displays Generated						
	Stats Analysis			Summary		Individual	
	T	F	L	T	F	F	L
AE Analyses							
All AEs				Y			Y
Grade 2 or higher AEs				Y			Y
SAEs				Y			Y
AE leading to treatment discontinuation or study withdrawal				Y			Y
Drug-related AEs				Y			
Drug-related SAEs				Y			
Drug-related Grade 2 or higher AEs				Y			
Common AEs				Y			
Common non-serious AEs				Y			
Common Grade 2-4 AEs				Y			
Common drug-related Grade 2-4 AEs				Y			
Laboratory Tests							
Grade 2 or higher laboratory events				Y			
Clinical Chemistry				Y			Y
Hematology				Y			Y
Fasting Lipid Profile				Y			Y
Urinalysis				Y			Y
Coagulation Profile				Y			Y
Other lab data including local lab							Y
Vital Sign Analysis							
Vital Signs				Y			Y
Death Analysis							
Death							Y

NOTES:

- T = Table, F = Figure, L = Listing, Y = Yes display generated.
- Stats Analysis = Represents TFL related to any formal statistical analyses (i.e. modelling) conducted.
- Summary = Represents TFL related to any summaries (i.e. descriptive statistics) of the observed raw data.
- Individual = Represents FL related to any displays of individual subject observed raw data.

8.3. Acceptability of CAB LA

The secondary acceptability analyses will be based on safety population, unless otherwise specified. All summary data and statistics are calculated from available data, unless otherwise specified.

To assess acceptability of the CAB LA, the proportion (with 95% confidence interval) of participants who would consider using CAB LA for HIV prevention in the future will be calculated among all subjects in the safety population (including those who terminated product use during the trial). Participants will be asked if they would consider using CAB LA for HIV prevention in the future at their Week 41 visit or at their withdrawal visit, whichever occurs first. Patients who are lost to follow up or with missing responses will be presented as such in a separate category.

Table 14 provides an overview of the planned acceptability analyses, with further details of data displays being presented in Appendix 14: List of Data Displays.

Table 14 Overview of Planned Acceptability Analyses

Display Type	Data Displays Generated						
	Stats Analysis			Summary		Individual	
	T	F	L	T	F	F	L
Acceptability of the CAB LA							
participants who would consider using CAB LA				Y			Y

NOTES:

- T = Table, F = Figure, L = Listing, Y = Yes display generated.
- Stats Analysis = Represents TFL related to any formal statistical analyses (i.e. modelling) conducted.
- Summary = Represents TFL related to any summaries (i.e. descriptive statistics) of the observed raw data.
- Individual = Represents FL related to any displays of individual subject observed raw data.

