Two Phase 2A PrEP studies have assessed potential CAB LA regimens for evaluation in Phase 3 PrEP trials. The first was a randomized, placebo-controlled, double-blind, multicenter US study (Study 201120, ECLAIR) in healthy men at low risk of acquiring HIV-1 to assess the safety, tolerability, acceptability, and PK of CAB LA given intramuscularly (IM). Participants were randomized in a 5 to 1 ratio to receive oral CAB 30 mg daily or matching placebo for 4 weeks. Following a safety assessment, participants received three CAB long-acting (LA) 800 mg (2 x 400 mg split IM injection) or saline intramuscular IM injections at 12-week intervals. Most participants (CAB LA, n=106; placebo, n=21) were MSM (83%) and Caucasian (56%). During the injection phase, Grade 2 or higher adverse events were experienced by more participants in the CAB LA group (n=75 [80%]) compared with placebo (n=10 [48%]; p<0.01), with the majority attributed to injection-site pain (CAB LA, n=55 participants [59%]; none with placebo). The median duration of injection site pain was 5.4 days. Only 4 participants terminated participation prematurely due to injection intolerance. Geometric mean trough concentrations were lower than predicted and did not achieve the target presumed to offer clinical benefit. Overall, 68 participants (79%) reported willingness to continue

CAB LA injections. In this US study CAB LA injection was well tolerated through Week 41, despite the high incidence of mild-to-moderate injection-site reactions.

HPTN077 (201103), an analogous study to ECLAIR, is an ongoing Phase 2 study evaluating PK and safety of CAB LA in men and women at low risk of HIV acquisition. Two regimens are being assessed in separate cohorts, including 800mg IM Q12W for three doses as well as CAB LA 600mg IM Q8W, with a second dose 4weeks following an initial 600mg IM dose, for a total of five doses. The Q8W regimen was selected based on modeling and simulation that included data from Phase 2 PrEP and treatment studies and was predicted to achieve clinical targets in male and female subjects. This study will evaluate the selected Phase 3 CAB LA 600 mg IM Q8W PreP dosing regimen in Chinese male adults of low risk of HIV acquisition prior to initiating PrEP trials in those of higher risk of infection.

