4. OBJECTIVES AND ENDPOINTS

Objectives	Endpoints
Primary	
Evaluate the safety and tolerability of the injectable agent, cabotegravir (GSK1265744) long acting (CAB LA) injectable (600 mg dose administered every 4 weeks for 2 doses followed by every 8 weeks for 3 doses) through Week 5-41 in HIV-1 uninfected Chinese men.	Safety and tolerability parameters, including adverse events, clinical laboratory tests, study withdrawals due to AEs, vital signs assessments, and evaluation of injection site reactions (ISRs).
Evaluate the plasma pharmacokinetics of CAB following repeat oral administration (Day 1 to Week 4) and CAB LA IM injections throughout the Injection Phase (Weeks 5-41).	Plasma CAB PK parameters following repeated once daily oral administration (Day1-Week 4) include (as permitted by the data): C_{τ} , $AUC(0-\tau)$, C_{max} , t_{max} , CL/F , V_{ss} , $t_{1/2}$, and λ_z . Plasma CAB PK parameters following CAB LA IM administration (Week 5-Week 41) include (as permitted by the data): C_{τ} , $AUC(0-\tau)$, C_{max} and t_{max} .
Secondary	
Evaluate the plasma pharmacokinetics of CAB LA through the Injection and Long-term Follow-up Phases (Week 5-89)	Plasma CAB PK parameters following CAB LA IM administration (Week 5 - Week 89) as permitted by the data including C_{τ} , $AUC(0-\tau)$, C_{max} , t_{max} , CL/F , V_{ss} , $t_{1/2}$, and λ_z .
Evaluate the safety and tolerability of oral CAB in HIV uninfected Chinese men during the oral lead-in Phase (Day 1 to Week 4)	Safety and tolerability parameters, including adverse events, study withdrawals due to AEs, vital signs assessments and clinical laboratory assessments.
Evaluate the acceptability of CAB LA injections through 41 weeks.	Injection discontinuation rate, the number and severity of ISRs and additional acceptability measures.
Explore concentration-effect relationships for various safety and tolerability parameters if relevant.	Evaluation of relationships between significant safety and tolerability parameters and CAB PK may be explored.

AE: Adverse events, $AUC(0-\tau)$: Area under the plasma concentration time curve over the dosing interval, C_{τ} : Concentration at the end of the dosing interval, C_{max} : Maximum observed concentration, T_{max} : Time of occurrence of C_{max} , τ : Dosing interval, λ_z : Apparent terminal phase rate constant, CL/F : Oral clearance, V_{ss} : volume of distribution at steady state, $t_{1/2}$: Terminal absorption elimination half-life.

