5.2. Number of Participants

Approximately 60 participants will be screened in order to ensure that approximately 48 participants will enter the oral phase and approximately 40 participants will enter the injection phase of the study. The participants will be enrolled from multiple sites in China. Participation will be limited to participants who are male at birth, with a target of at least 60% men who have sex with men. For further details, refer to Section 10.

If participants prematurely discontinue the oral phase of the study, additional replacement participants may be recruited at the discretion of the Sponsor. Participants who enter the injection phase of the study will not be replaced.

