10.3.2. Secondary Analyses

Acceptability

To assess acceptability of the CAB LA, the proportion (with 95% CI) of participants who would consider using CAB LA for HIV prevention in the future will be calculated among all enrolled participants (including those who terminated product use during the trial). Participants will be asked if they would consider using CAB LA for HIV prevention in the future at their Week 41 visit or at their withdrawal visit, whichever occurs first.

Tolerability

To assess tolerability of CAB LA, the proportion of participants who terminate from receiving injections prior to the full course due to AE, intolerability of injection, frequency of injections, or burden of procedures related to injections out of those participants that received at least one injection.

A questionnaire will also be used to assess participant tolerability and satisfaction to the treatment. For each question the responses will be summarized by the proportion of participants reporting the response out of all those that answered the question. An overall treatment satisfaction score will be calculated for each participant.

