4. ANALYSIS POPULATIONS

Population	Definition / Criteria	Analyses Evaluated
All Subjects Screened	
 Comprise of all subjects who consent to participate in the clinical study. 	
 Disposition summary
Safety	
 Comprise of all subjects who receive at least one dose of the study treatment. 	
 All demographic General safety analyses Safety analysis for the oral phase Analysis of acceptability of CAB LA
Safety Injection	
 Comprise of all subjects received at least one CAB LA injection 	
 Safety and tolerability analyses of CAB LA in primary and extended analyses
Oral Pharmacokinetic (PK)	
 Will consist of all subjects in the 'Safety population' for whom an intensive oral pharmacokinetic sample was obtained and analysed. PK samples that may be affected by protocol deviations will be reviewed by the study team to determine whether or not the sample will be excluded. 	
 Oral PK Concentration Oral PK Parameters
Injection (Week 41) Pharmacokinetic (PK)	
 Will consist of all subjects in the 'Safety population' for whom an injection pharmacokinetic sample was obtained and analysed during Weeks 5 to 41. PK samples that may be affected by protocol deviations will be reviewed by the study team to determine whether or not the sample will be excluded. 	
 Injection PK Concentration Injection PK Parameters
Injection (Week 89) Pharmacokinetic (PK)	
 Will consist of all subjects in the 'Safety population' for whom an injection pharmacokinetic sample was obtained and analysed during Weeks 5 to 89. PK samples that may be affected by protocol deviations will be reviewed by the study team to determine whether or not the sample will be excluded. 	
 Injection PK Concentration Injection PK Parameters

NOTES:

Please refer to [Appendix 14](#): List of Data Displays which details the population to be used for each display being generated.

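### The proportion who would use CAB LA in future is planned only on a base that includes men never injected, so add a row for injected men and a rule for missing answers

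*SAP*

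**What the plan says.** Protocol section 4 lists as a secondary objective: "Evaluate the acceptability of CAB LA injections through 41 weeks". One measure serving it is whether a man would consider CAB LA for HIV prevention in future. Protocol 10.3.2 says that this proportion "will be calculated among all enrolled participants (including those who terminated product use during the trial").

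SAP 8.3 carries the rule over to the Safety population: the proportion "will be calculated among all subjects in the safety population (including those who terminated product use during the trial"). SAP section 4 defines that population as follows: "Comprise of all subjects who receive at least one dose of the study treatment". Oral CAB comes first, so a single tablet qualifies. Table 2.29 in the SAP's list of displays also names the Safety population.

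The question is put to participants "at their Week 41 visit or at their withdrawal visit, whichever occurs first". SAP 8.3 shows lost-to-follow-up and missing answers as their own category. It also says that statistics rest on available data unless specified otherwise.

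Protocol 5.2 plans that "approximately 48 participants will enter the oral phase and approximately 40 participants will enter the injection phase of the study". It adds that, for men who leave in the oral phase, "additional replacement participants may be recruited at the discretion of the Sponsor".

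SAP section 4 also defines a Safety Injection population, meaning men with at least one CAB LA injection. It is used for injection site reactions (SAP 7.1.1, Table 2.2), for the injection discontinuation rate (SAP 7.2) and for the satisfaction score (SAP 7.2, Table 2.28), but not for the willingness question.

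**The concern.** The objective concerns injections, while the denominator takes in men who have only swallowed tablets. A man can leave during the oral phase for reasons unrelated to the injection, such as a liver stopping criterion, PrEP use or a change in HIV risk (protocol 8.1.1 and 8.2.1). If such men give no answer and stay in the denominator, lead-in drop-out is read as lower acceptability. If they do answer, they rate a product that they have not tried.

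The other measures that protocol section 4 names under this objective, injection discontinuation and injection site reactions, are reported in injected men. The willingness figure is the only direct measure of whether a man would use CAB LA again, and as planned it will not be shown for men who used it.

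There is a second gap. The SAP does not settle whether unanswered questions stay in the denominator, so two analysts could report different percentages from the same data.

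**Working it through.** There is no planned value to reproduce. The endpoint is descriptive, and neither document states an expected proportion.

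**Inputs**
- Men entering the oral phase: about 48 (protocol 5.2).
- Men entering the injection phase: about 40 (protocol 5.2).
- Yes answers among the 40 injected men: x. The value x = 32 is an assumption for illustration.
- Yes answers among the never-injected men: k, which can be anything from 0 to 8.

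**Never-injected share of the denominator**
- 48 − 40 = 8, and 8/48 = 16.7%.
- Both counts are approximate. If 45 to 50 men enter the oral phase and 38 to 42 are injected (an assumed range), the share runs from 3/45 = 6.7% to 12/50 = 24%.
- A replaced drop-out stays in the Safety population, so the number is not capped at 8.

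**Reported value with all 48 in the denominator: (x + k)/48**

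Among injected men, 32/40 = 80.0% (exact Clopper-Pearson 95% CI 64.4 to 90.9).

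| Never-injected men counted as yes | Calculation | Reported value | Exact 95% CI |
|---|---|---|---|
| 0 | 32/48 | 66.7% | 51.6 to 79.6 |
| 4 | 36/48 | 75.0% | 60.4 to 86.4 |
| 8 | 40/48 | 83.3% | 69.8 to 92.5 |

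**Direction**
- Reported value minus injected value = (8/48) × (k/8 − x/40).
- With x = 32, this runs from (1/6) × (0 − 0.80) = −13.3 points to (1/6) × (1 − 0.80) = +3.3 points.
- The two values agree when k/8 = 0.80, that is k = 6.4. The sign therefore depends only on whether never-injected men say yes less or more often than injected men.

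**Largest relative understatement**
- With k = 0 and all 8 retained, (x/48) ÷ (x/40) = 40/48 = 0.833.
- The loss is 1 − 0.833 = one sixth, whatever x is. It is a relative figure, not a fixed number of percentage points.

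**Effect of the missing-answer rule alone**
- Suppose none of the 8 answers. If they stay in the denominator, the result is 32/48 = 66.7%. If they leave it, the result is 32/40 = 80.0%.
- The same data give results 13.3 points apart, and SAP 8.3 does not choose between them.

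**The case against.** The denominator was specified in advance in the protocol, and SAP 8.3 implements it. The question looks forward, so a man who was never injected can answer it, and the withdrawal visit gives him the occasion. In this trial the injections follow an oral lead-in, so a man who stops on tablets has left the regimen on offer. Restricting to injected men conditions on something that happens after enrolment and answers a different question. Discontinuation of injections, site reactions and the satisfaction score can only be measured in injected men, so a different base for willingness is not in itself inconsistent. The endpoint is descriptive and secondary. Disposition by phase and the individual answers in Listing 38 would let a reader rebuild the injected-only figure.

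Most of this stands. It is a good reason to keep the all-enrolled row and not to replace it. It does not remove the case for showing the injected-only figure, because the objective is worded about injections and a reader should not have to rebuild the figure from listings. Nor does it touch the unsettled rule for missing answers.

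Two stronger readings are tempting and not supported:
- **That the planned figure must understate acceptability.** This needs never-injected men to say yes less often than injected men, or to be kept in the denominator unanswered. Neither is established, and the figure can also come out too high.
- **That the plan fails to match a 79% benchmark.** Protocol 3.2 reports of an earlier US study: "Overall, 68 participants (79%) reported willingness to continue". This is background, neither document makes it a target, and it concerns continuing injections, not considering future use. Its denominator is not stated. The only whole number that fits is 86 (68/86 = 79.1%). The same paragraph's 75 men at 80% implies 94 injected men, and 68/94 = 72.3%, while 68 of the 106 men in the CAB LA group is 64.2%. Neither an injected nor an all-allocated base reproduces 79%, so it cannot decide between them.

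**Conclusion.** The point holds as a low-cost improvement to a descriptive secondary analysis. It is not an error in the plan or a departure from the protocol. At the planned numbers, about one in six men in the denominator never receives the product being rated. With 80.0% yes among injected men, the reported value could lie anywhere from 66.7% to 83.3%. The one-sixth relative understatement is the worst case only: it requires that no never-injected man counts as a yes and that all of them remain in the denominator. These sizes rest on the approximate 48 and 40, on the illustrative 32 of 40, and on no extra never-injected men entering through replacement.

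**What to change.** In SAP 8.3 and Table 2.29:
- Keep the protocol-defined all-enrolled (Safety population) row, labelled as such.
- Add the proportion with its 95% CI in the Safety Injection population, including men who later stopped injections. Name this as the figure used to interpret acceptability among users.
- State for each row whether lost-to-follow-up and missing answers count in the denominator.

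Declare the addition in SAP 2.1. No new data or population is needed. The cost is a few sentences, one table row and a declared addition to the protocol's analysis.

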8.4. Concentration-effect Relationships for Safety and Tolerability Parameters

Evaluation of relationships between significant safety and tolerability parameters and CAB PK may be explored.

8.5. General Safety Analyses

This section will describe safety analyses that are not mentioned in Section 7.1 or Section 8.2, but usually are performed as safety assessment.

